## 4.7.2 Major secondary outcomes

- 1) Composite maternal cardiovascular and other morbidity: Death, any new heart failure, stroke or encephalopathy, Ml/angina, pulmonary edema, ICU admission/intubation, encephalopathy, or renal failure.
- 2) Persistent severe maternal hypertension (with or without proteinuria) + components of the primary composite endpoint
- 3) Preterm birth and Indicated preterm birth (<37 weeks)
- 4) Composite of severe neonatal morbidities: Bronchopulmonary dysplasia (BPD), Retinopathy of prematurity (ROP), Necrotizing enterocolitis (NEC), Intraventricular hemorrhage (VH) grade III/IV.

The following outcomes will be evaluated in secondary studies:

- 5) Timing of delivery outcomes: The risks of 3 key outcomes, a) perinatal death, b) composite neonatal morbidity and c) composite of severe maternal morbidity (defined above) will be examined in relation to gestational age (completed weeks from 36 to 40 weeks) using longitudinal analysis methods to determine the delivery gestational age at which risks nadir (see analysis section).
- 6) Biospecimen collection: i) Maternal whole blood, plasma, paxgene and serum at the time of randomization and midtrimester (24-30 weeks), ii) cord blood (whole blood, serum and plasma) at time of delivery, iii)

- placenta collected and sent to pathology for routine clinical evaluation. All maternal and cord blood specimens will be frozen at -80 degrees C for future studies.
- 7) These future biospecimens studies will include a comprehensive assessment of the role and interactions of clinical, biological and biophysical factors (e.g., BP levels, maternal obesity, smoking, glucose intolerance, hyperlipidemia, genes/pharmacogenetics and ultrasound findings) on the occurrence and severity of preeclampsia, SGA and other outcomes.
- 8) Adherence to treatment at 6 (4-12) weeks postpartum: The follow-up questionnaire will include items to assess adherence to antihypertensive therapy since delivery.

#### 4.7.3 Other maternal outcomes

- 1. Superimposed Preeclampsia (mild or severe including eclampsia)
- 2. Superimposed gestational hypertension (persistent hypertension above baseline without proteinuria occurring after 20 week's gestation).
- 3. Serial maternal systolic and diastolic BP (mean values and changes during pregnancy should differ between groups if the intervention is successful). Both the pragmatic clinic and standardized automated/Omron BPs will be assessed.
  - 4. Severe hypertension (treatment needed)
  - 5. Cesarean delivery
  - **6.** Blood transfusion (during pregnancy or postpartum)

#### 4.7.4 Other newborn outcomes:

- 1) NICU admission and stay
- 2) Low birth weight (<2500g)
- 3) Ponderal index (wt/ht)
- 4) Head circumference
- 5) Placental weight
- 6) Hypoglycemia
- 7) Bradycardia
- 8) Hypotension
- 9) Other neonatal morbidities (including respiratory distress syndrome, transient tachypnea of the newborn intubation/ventilation, seizures, hyperbilirubinemia, 5-min Apgar score <7and sepsis)

#### 4.7.5 Health care resource utilization outcomes (these will be reported in secondary studies):

- 1) Prenatal clinic/ER visits
- 2) Prenatal hospitalizations
- 3) Delivery hospital stay (maternal/newborn)
- 4) Postpartum unscheduled/ER visits

#### 5) Postpartum hospitalizations

#### 4.7.6 Follow-up and Outcome Ascertainment Periods:

The primary outcomes will be ascertained from randomization until discharge from the delivery hospitalization and two weeks postpartum. For newborns who are not discharged from the hospital, neonatal death will be ascertained until 90 postnatal days. Secondary and other maternal/infant outcomes including BP control, treatment adherence, readmissions and ER/unscheduled visits and related diagnoses will be measured at a 6 week (4-12 weeks) postpartum visit. Records of such encounters will be obtained for review.

Planned long-term follow-up: We will plan for participants to be contacted by phone at 6 months to ascertain maternal and infant status. This phone contact will also facilitate anticipated follow-up study of the trial cohort (involving in-person visits annually) to determine long-term maternal and infant outcomes in relation to anti-hypertensive therapy during pregnancy. Key maternal outcomes include BP control, treatment adherence and cardiovascular outcomes; infant/child outcomes for such a separate study would include growth, neurodevelopment and metabolic outcomes by treatment status.

**Central review of outcomes:** Coordinated by the DCC and an outcomes adjudication committee, 2-3 site PIs will conduct a blinded record review and validation of findings for all patients reported or suspected of having the primary and selected major secondary outcomes.

#### 5 Statistical considerations

#### 5.1 Sample size for Primary outcome

The original sample size for the study (n=4700) was based on the rationale provided in section 5.1.1 below. A proposal to reduce the sample size for the primary outcome was initiated in 2016. The proposal was based on an evaluation of primary outcomes of the first 800 consecutive patients enrolled in the study, and based on a blinded sample size reassessment (SSR). The sample size based on this SSR was formally reduced to 2404 in December, 2018. The rationale is provided in section 5.1.2 below.

#### 5.1.1 Original Sample Size

We used data from the MFMU Network's High Risk Aspirin study (enrollment into the CHTN group was based on pragmatic clinic BPs) to estimate the frequency of the composite outcome components among 763 women with mild CHTN at baseline as follows: Fetal or neonatal death = 6.16%; severe preeclampsia (severe hypertension and proteinuria, eclampsia, preeclampsia with thrombocytopenia, creatinine>1.4, elevated liver enzymes) =0.66%; abruption =1.46%; indicated PTB <35 weeks =12.32%. The frequency of the primary composite outcome was 16%. Assuming a 2-sided alpha of 0.05 and conservative baseline incidence of 16% (since this is regardless of BP lowering therapy, and we expect the incidence to be higher in those not receiving therapy) the unadjusted sample sizes/arm needed to detect a 20-30% reduction in the primary outcome with 85-90% power are presented in Table 5. These unadjusted estimates do not take into account drop-ins and drop-outs or the interim look we propose. We assume: the 10% of the control group that will require treatment for severe hypertension are already well-accounted for in our baseline rate of 16% estimated from usual care; that in addition there will be up to a 10% rate of protocol violations (treatment in the control group without meeting criteria for severe hypertension) and that nonadherence in the treatment arm is 10%. The adjusted outcome rates for 25% reduction are: 15.6% and 12.4%, and the revised adjusted sample sizes/arm accounting additionally for 8% loss-to-follow up are presented in Table 5.

Table 5: Estimated sample size/arm (30%, 25% and 20% Reductions) under original plan

	30% REDUCTION		25% REDUCTION		20% REDUCTION	
Power	Unadjusted	Adjusted	Unadjusted	Adjusted	Unadjusted	Adjusted
90%	1075	1829	1587	2696	2539	4314
85%	919	1561	1356	2305	2170	3687

The adjustment factors are based on studies of US populations. In one trial of therapy for mild CHTN, 10% of women in the control group required treatment for severe hypertension and treatment nonadherence or protocol violations occurred in 10%.  Our collective experience (mainly as sites of MFMU intervention studies) indicates treatment adherence rates of 80-90% among pregnant women and loss-to-follow-up rates of 5% or less.  **Therefore, 2350/arm or a total sample of 4700** will provide 85-90% power to detect at least a 2-sided 25% effect size for the primary outcome. The sample size is large, as desirable for a pragmatic trial. The detectable

effect size will be 20% or less with >85-90% power if nonadherence, treatment crossover, protocol violations and losses to follow-up occur less frequently than anticipated. DSMB monitoring will allow us to stop early for benefit and safety, but only one formal interim look is planned at this time. \*In addition, we propose an adaptive sample size: if the DSMB determines on interim review that a size larger than 4700 is needed, we will increase the sample size by up to 1000 based on their recommendation.

## 5.1.2 Revised Sample Size

The original sample size was based on a 25% reduction in the primary composite outcome. Reductions as high as 30% and as low as 20% were also considered. At the time of the original protocol, the 30% reduction in the composite outcome rate was justified on the basis of other studies where reductions of 33% or greater were seen. However, these reductions were examined post hoc and from epidemiological studies and small trials. The original proposal also anticipated a high eligibility rate, estimating that 25% of screened patients would be enrolled. Thus, given these two factors a conservative 25% rate reduction was selected.

Based on studies published following the approval of the CHAP trial, it was hypothesized that the overall event rate for the CHAP study was underestimated along with the expected reduction in the primary outcome. In addition, participant accrual during the trial was slower than anticipated, arising from the underestimation of the yield from screening to randomization. A revised sample size (n=2404) was proposed that incorporated a larger 33% reduction in the primary outcome and thus reflected a more feasibly attainable target sample size. The total sample size of 2404 reflects a 33% reduction in the primary outcome (from a baseline rate of 16%), 10% noncompliance and crossover, and 85% power. As seen in Table 6 below, the necessary sample size per group is 1142 when incorporating these criteria; accounting for 5% attrition inflates the sample size per group to 1202 (n=2404 total).

Table 6: Estimated sample size/arm (33%, 30% and 25% Reductions) under revised plan as of January 2019

	33% REDUCTION		30% REDUCTION		25% REDUCTION	
Power	Unadjusted	Adjusted	Unadjusted	Adjusted	Unadjusted	Adjusted
90%	868	1336	1075	1829	1587	2696
85%	748	1142	919	1561	1356	2305

Based on this revised sample size, it was decided to perform a blinded SSR based on the overall study composite outcome rate and assumptions as noted above. The blinded SSR examined internal study data in order to evaluate whether assumptions used for the original sample size were consistent with an underestimated composite outcome rate and whether the revised minimum target sample size of 2404 was sufficient. Complete details are provided in a separate Statistical Analysis Plan (SAP) and details are part of records of the December

2018 DSMB Report. Briefly, the overall event rate was determined by evaluating the primary outcome event rate in first 800 women enrolled into the trial. A 95% confidence interval for this composite outcome rate was also determined. Rates by study group were not examined in order to maintain the blinded SSR and avoid repeated statistical testing and inflation of the overall alpha level. The DCC estimated the event rates in the two combined trial groups based on the observed overall rate and under multiple hypothesized rate reductions. In addition, the DCC estimated the event rates in the two trial groups based on the lower bound of the 95% confidence interval for the overall rate and under multiple hypothesized rate reductions. This allowed data accrued early in the trial to provide a range of plausible event rates observable during the trial. Sample sizes needed to achieve at least 85% power based on these rates were then evaluated and compared with the proposed minimum sample size of 2404.

The formal SSR was performed and presented to the DSMB and NHLBI in 2018. In order to preserve confidentiality and any potential impact on equipoise, the actual numbers presented are withheld from this report (but they are intended to be published in a manuscript describing the study's design when enrollment is complete). In summary, the overall event rate was higher than that originally expected and the derived event rate in the untreated group was estimated to be higher than the 16% originally hypothesized. Furthermore, it was determined that the revised sample size of 1202 per group (n=2404 total) would indeed provide at least 85% power for the primary outcome for reductions as low as 25%.

#### 5.2 Power for other outcomes

The sample size of 2404 provides adequate power to examine SGA and key secondary outcomes. The corresponding power for each outcome considering conservative estimates of baseline incidence and effect sizes given a 2-sided alpha of 0.05 are shown in Table 7.

Table 7: Power – SGA and Secondary Outcomes

Outcome	Incidence	Effect size %	Power
SGA	10-14%	35-40	≥85%
Preeclampsia	20%	25	>85%
Cardiovascular	4-6%	50	80-90%
Preterm birth	20%	25	>85%
Perinatal death	4-6%	50	80-90%

The baseline risks of SGA, preeclampsia, preterm birth and perinatal death are likely to be higher considering the reviewed literature and our preliminary data--power may actually be higher. The incidence of the rare maternal cardiovascular outcome is not well characterized. This study will provide an estimate. Finally, regarding the repository, we anticipate collecting baseline and follow-up biospecimens (especially maternal and cord blood) on ≥80% (n=1920).

c) Baseline/covariate information: These will include demographics (age, parity, ethnicity, education, profession, payor), entry GA at entry, entry BP, duration of CHTN, treatment status on entry, prior preeclampsia, prior fetal death, BMI, smoking/alcohol/drug use.

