#### 2.4 CHTN and Increased Adverse Obstetric Outcomes:

CHTN is associated with a 3- to 5-fold increase in several adverse pregnancy outcomes including superimposed preeclampsia. (See Table 1 for incidence and relative risks compared to those without CHTN):

Preeclampsia: Superimposed preeclampsia complicates 25-30% of pregnancies in women with CHTN and is a strong predictor of other adverse outcomes. The risk appears to be increased in those with a longer history of CHTN or with a prior history of preeclampsia.

Table 1: Adverse perinatal outcomes in CHTN patients

Outcome	Incidence %	RR (vs. no CHTN)*
Preeclampsia	25-30	3-4 
IUGR/SGA	11	2-3 
Abruption	1.5	2-3 
PTB <37 wk	38-50	3-4 
<35 wk	18-22	
Perinatal death	6-8	3-5 

\*RR or OR relative to no CHTN based on referenced reports

b) Perinatal morbidity: CHTN is associated with a marked increase in adverse outcomes (Table 1), including perinatal death, small for gestational age (SGA), placental abruption, and preterm birth (PTB). As many as a third of women with CHTN have been reported to have poor fetal growth, and over 50% to have PTB. The risk of adverse outcomes is particularly high among those who develop preeclampsia. Neonatal morbidity is also increased in offspring of women with CHTN, as reflected by a 24.3% incidence of NICU admission in the MFMU High Risk Aspirin trial.The risk of cesarean delivery (increasing maternal morbidity in current and future pregnancies) is increased 2-fold. Preeclampsia is associated with a 2-3 fold increase in the risk of maternal death (particularly among African Americans) and is among the top 3 causes of maternal death in the US. These significant risks are present in women with mild CHTN; the risks of preeclampsia and perinatal mortality among women with mild CHTN are at least 2-3 fold higher compared to women without CHTN.

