Based on studies published following the approval of the CHAP trial, it was hypothesized that the overall event rate for the CHAP study was underestimated along with the expected reduction in the primary outcome. In addition, participant accrual during the trial was slower than anticipated, arising from the underestimation of the yield from screening to randomization. A revised sample size (n=2404) was proposed that incorporated a larger 33% reduction in the primary outcome and thus reflected a more feasibly attainable target sample size. The total sample size of 2404 reflects a 33% reduction in the primary outcome (from a baseline rate of 16%), 10% noncompliance, 10% crossover, and 85% power. As seen in Table 2 below, the necessary sample size per group is 1142 when incorporating these criteria; accounting for 5% attrition inflates the sample size per group to 1202 (n=2404 total).

Table 2: Estimated sample size/arm (33%, 30nd 25% Reductions) under revised plan as of January 2019

	33% REDUCTION		30% REDUCTION		25% REDUCTION	
Power	Unadjusted	Adjusted	Unadjusted	Adjusted	Unadjusted	Adjusted
90%	868	1336	1075	1829	1587	2696
85%	748	1142	919	1561	1356	2305

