## 3.2. Primary Hypothesis #2: Impact of Blood Pressure Treatment on Poor Fetal Growth (i.e. SGA<10th percentile based on birth weight)

 $H_0$ : There will be no difference in the rate of poor fetal growth in CHAP participants treated in the Low BP group therapy compared to participants in the Standard BP group.

- **3.2.1. Poor Fetal Growth Outcome:** We will examine small for gestational age (SGA) infants identified as <10th percentile based on birth weight at the delivery gestational age. SGA has not been included in the composite, because the concerns that therapy may be a cause (impaired placental blood flow) of SGA, it is assessed separately as the primary safety outcome to evaluate harms. *The two primary hypotheses provide clear endpoints for benefit versus harm. Based on our preliminary data, however, BP control may be associated with a reduction in risk of SGA*. A national standard weight curve presently planned to be Alexander's, but may be modified prior to data closure with another acceptable customized curve used to identify SGA infants at the time of analysis. We will also, secondarily, examine extreme SGA <5th and <3rd percentiles.
- **3.2.2. Analysis Plan:** The  $\chi^2$  test of association will be used to evaluate whether the rate of the SGA differs between the two blood pressure management approaches. The primary analysis will follow the

analysis plan for the composite primary outcome. Specifically, for cases where the primary composite outcome is undetermined (for example, dropout prior to delivery), the primary analysis will utilize multiple imputation based on the characteristics within treatment group that are predictive of the SGA outcome. Logistic regression models will be fit within treatment group using baseline characteristics predictive of the SGA outcome and this group-specific model will be used to provide the imputed outcome values. Up to 5 replicates will be considered. All individuals will be analyzed as randomized to the two treatment groups, regardless of whether they adhered to their assigned treatment. Sensitivity analyses will follow the primary outcome analysis plan described above. Relative rates (RR) and 95% confidence intervals (CIs) will be computed and presented, as well as individual group rates and 95% CIs. In the event of imbalanced patient characteristics in the two groups, multivariable modeling will be performed as described in the previous section.

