**3.2.3. Power for other outcomes:** The sample size of 2404 provides adequate power to examine SGA and key components of the primary outcome separately. The corresponding power for each outcome considering conservative estimates of baseline incidence and effect sizes given a 2-sided alpha of 0.05 are shown in Table 3.

Table 3: Power – SGA and Secondary Outcomes

Outcome	Incidence	Effect size %	Power
SGA	10-14%	35-40	≥85%
Preeclampsia	20%	25	>85%
Cardiovascular	4-6%	50	80-90%
Preterm birth	20%	25	>85%
Perinatal death	4-6%	50	80-90%

The baseline risks of SGA, preeclampsia, preterm birth and perinatal death are likely to be higher considering the literature reviewed and our preliminary data, thus power may actually be higher. The incidence of the rare maternal cardiovascular outcome is not well characterized. This study will provide a more precise estimate and will consider any new heart failure, stroke or encephalopathy, and MI/angina as cardiovascular outcomes.

**3.3 Interim Monitoring**: The study investigators, in conjunction with the study DSMB and NHLBI, propose 1 interim analysis for the CHAP trial. In order to maintain maximum power for the final analysis, and to simultaneously protect the overall type I error of the study, we propose that alpha levels at the interim analysis be selected using a Lan-DeMets alpha spending function that follows O'Brien-Fleming boundaries.

The formal interim analysis will be conducted when 50% (n=1202) of the total sample size (n=2404) has completed the study. The first 1202 consecutive women enrolled in the study will be reviewed for primary outcomes following their last study visits. All suspected primary outcomes included in the composite primary outcome will undergo review for adjudication. The interim analysis will focus on the analysis of these adjudicated outcomes. Group totals and rates will be presented in a masked fashion (using A and B labels rather than actual treatment assignment labels), where only the study statistician will know the true identity of A and B. The masked labels will be removed and true group assignments revealed only upon request by the DSMB.

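### The stated power for SGA and the secondary outcomes omits the noncompliance and crossover applied to the primary outcome, and for SGA it does not cover an increase at the lower end of the tabulated range

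*Combined protocol and SAP*

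**What the plan says.** Protocol 5.2 states "The sample size of 2404 provides adequate power to examine SGA and key secondary outcomes". SAP 3.2.3 makes a similar claim for a slightly different set of outcomes: "The sample size of 2404 provides adequate power to examine SGA and key components of the primary outcome separately". Both rest on the same five rows, at two-sided alpha 0.05:

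- SGA: incidence 10–14%, effect 35–40%, power ≥85%
- Preeclampsia, and preterm birth: 20%, 25%, >85%
- Cardiovascular, and perinatal death: 4–6%, 50%, 80–90%

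Neither section mentions adherence, crossover or attrition for these rows, and the effect column carries no sign. The inputs are called conservative, and baseline risks other than the cardiovascular one "are likely to be higher considering the reviewed literature and our preliminary data".

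The primary outcome is handled differently. Protocol 5.1.1 starts from a full-adherence reduction and dilutes it for 10% treatment in the control arm and 10% nonadherence in the treated arm: "The adjusted outcome rates for 25% reduction are: 15.6% and 12.4" percent. The revised plan keeps this. Protocol 5.1.2 lists "10% noncompliance and crossover, and 85% power", and SAP 3.1.4 lists "10% noncompliance, 10% crossover, and 85% power".

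On the role of SGA, SAP 3.2.1 says "it is assessed separately as the primary safety outcome to evaluate harms".

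**The concern.** Noncompliance and crossover belong to the trial, not to one endpoint. All outcomes come from the same women, analyzed as randomized, so a full-adherence effect on preeclampsia or SGA is diluted just as one on the composite is. If the tabulated effects are of that kind, as the 25% and 33% reductions for the composite are, the powers correspond to the columns headed Unadjusted in the plan's own primary-outcome tables and are too high.

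Direction matters for SGA in particular. At the same incidence and relative effect, an increase has less power than a reduction, because the higher event rate in the treated arm raises the variance. SGA is one of the two primary hypotheses and the one meant to detect harm. If the trial shows no significant difference in SGA, a reader will want to know what increase it could have detected, and the tables do not answer that.

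**Working it through.** **Inputs.** Two-sided alpha 0.05; 1202 randomized per arm; 1142 per arm before the 5% attrition allowance (Protocol 5.1.2). Rates and effects are from Protocol Table 7. Each range below runs from n = 1142 to n = 1202 per arm.

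**Formulas.** With control rate c, treated rate t and p = (c + t)/2:

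- Power = Φ{ [ |c − t| − 1.96·√(2p(1 − p)/n) ] / √( [c(1 − c) + t(1 − t)]/n ) }
- Dilution: c′ = 0.9c + 0.1t and t′ = 0.9t + 0.1c

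**Step 1: reproduce the plan's primary-outcome figures.**

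- 16% vs 12%, 85% power: 1350 per arm (stated 1356).
- Diluted: 0.9 × 16 + 0.1 × 12 = 15.6%, and 0.9 × 12 + 0.1 × 16 = 12.4%, as stated. With 8% loss this needs 2294 per arm (stated 2305).
- 16% with a 33% reduction, diluted: 15.47% vs 11.25%, needing 1164 per arm (stated 1142; an exact one-third reduction gives 1139).

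So the dilution rule is the plan's own.

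**Step 2: Table 7 as reductions, without and with that dilution.** Example for 20% with a 25% reduction, diluted, n = 1142: rates 19.5% and 15.5%, p = 17.5%. The null standard error is √(2 × 0.175 × 0.825/1142) = 0.01590 and the alternative one is 0.01588. Power = Φ[(0.04 − 1.96 × 0.01590)/0.01588] = Φ(0.556) = 71%.

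| Row | Stated | Undiluted | Diluted rates | Diluted power |
|---|---|---|---|---|
| Preeclampsia, preterm birth: 20%, −25% | >85% | 88–90% | 19.5 vs 15.5% | 71–73% |
| Cardiovascular, perinatal death: 4%, −50% | 80–90% | 80–82% | 3.8 vs 2.2% | 61–63% |
| Cardiovascular, perinatal death: 6%, −50% | 80–90% | 93–94% | 5.7 vs 3.3% | 79–81% |
| SGA 10%, −35% | ≥85% | 86–88% | 9.65 vs 6.85% | 68–70% |
| SGA 10%, −40% | ≥85% | 94–95% | 9.6 vs 6.4% | 80–82% |
| SGA 14%, −35% | ≥85% | 96% | 13.5 vs 9.6% | 83–85% |
| SGA 14%, −40% | ≥85% | 99% | 13.4 vs 9.0% | 92–94% |

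Undiluted, every stated floor is met. Diluted, most are missed, 6% with −50% sits at about its floor, and SGA at 14% with −40% still meets it.

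**Step 3: SGA as an increase.**

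| Pairing | Undiluted | Diluted |
|---|---|---|
| 10%, +35% | 74–76% | 55–57% |
| 10%, +40% | 84–86% | 65–68% |
| 14%, +35% | 88–90% | 72–74% |
| 14%, +40% | 95–96% | 82–84% |

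Smallest risk ratio detectable with 85% power at 1142 per arm: 1.41 at 10% and 1.33 at 14%; with dilution 1.52 and 1.42.

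**Step 4: diluted power at baseline risks cited elsewhere in the protocol.**

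- Preeclampsia 25% and 30% (section 2.4), −25%: 82–84% and 90–92%
- Preterm birth 38% (Table 1), −25%: 97–98%
- Perinatal death, halved: 5% (section 2.7.3) 71–73%; 6.16% (section 5.1.1) 80–82%; 8% (Table 1) 90–91%
- SGA 11% (Table 1, section 2.7.3): 73–75% at −35% and 84–86% at −40%

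**The case against.** The strongest reply is that no number in the table is wrong. Read as net intention-to-treat reductions, all the floors hold, and a reader can recover that basis by reproducing them. This stands: a reader might infer an arithmetic error, and there is none. What is missing is a statement of the basis, in a plan that uses a different basis for its primary outcome.

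Second, SGA does have a direction outside the tables. Protocol 1.2 and 3.1 list it among the outcomes that therapy is expected to reduce, and Protocol 4.7.1 and SAP 3.2.1 say that blood pressure control may lower it. That supports reading the row as a reduction. It does not supply power for the harm that the outcome is meant to evaluate.

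Third, the tabulated incidences are presented as conservative, and the documents give higher ones; for instance, "Superimposed preeclampsia complicates 25-30% of pregnancies in women with CHTN". This recovers much of the loss for preeclampsia and preterm birth, and perinatal death at 6.16% just reaches 80%. It does less for SGA at 11% or perinatal death at 5%.

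Fourth, 10% in each arm may be pessimistic, since Protocol 5.1.1 speaks of up to 10% violations. At 5% in each arm (my assumption, not a figure in the documents), power is 81–83% for the 20% rows, 78–80% for SGA at 10%/−35% and 71–74% for a halving from 4%, all still below the stated values.

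Finally, the SGA contrast in the chronic hypertension subgroup of the cited tight-control trial (13.9% vs 19.7%, Protocol 2.6.2.1) would be detected with 96–97% power, or 84–86% diluted. The gap therefore concerns smaller increases or lower baselines.

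**Conclusion.** The point holds as a conditional one, with minor weight. If the tabulated effects are full-adherence effects, as for the primary outcome, stated power is overstated at the tabulated incidences by roughly 12 to 19 percentage points in the rows hit hardest: 71–73% against >85%, 61–63% against a floor of 80%, and 68–70% against ≥85%. If they are net reductions, the floors stand and only the label is missing. On either reading, ≥85% does not cover an SGA increase over the whole tabulated range: 10%/+35% has 74–76% power undiluted, and the four corner pairings have 55–84% after dilution.

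This rests on a pooled two-proportion calculation, 1142 to 1202 per arm, and the plan's own 10%/10% rule.

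A reader might go further and infer that the trial is underpowered for these outcomes. The documents do not support that: the net reading is open, and several cited baselines restore the power. A reader might also object that net effects would imply full-adherence effects larger than the 33% assumed for the composite. These are different endpoints, so that comparison shows nothing. The tables set no sample size, analysis or stopping rule.

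**What to change.** In Protocol Table 7 and SAP Table 3, do one of two things: restate power at 1142 evaluable per arm with the 10%/10% dilution, or add a sentence that the effects are net intention-to-treat reductions. In either case add SGA power for an increase, or the smallest increase detectable with 85% power at 1142 per arm: a risk ratio of about 1.41 at 10% and 1.33 at 14%, or about 1.52 and 1.42 after dilution.

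The cost is two tables and a few sentences. The downside is less favorable stated power if the effects are full-adherence effects. No patients are added, and no analysis or stopping rule changes.
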